5.3 Safety Evaluations

Change in blood glucose level from baseline to more than 240 mg /dl or less than 70 mg /dl. Adverse events such as: Headach, Bloating or Minor abdominal pain Other Evaluations.

6 SUBJECT SELECTION

6.1 Study Population

Subjects with a diagnosis of pre-diabetic who meet the inclusion and exclusion criteria will be eligible for participation in this study.

6.2 Inclusion Criteria

1. Male or female ≥ 18 years of age at Visit 1.
2. Documentation of a pre-diabetic diagnosis as evidenced by one or more clinical features consistent with and one of the following criteria:
 - fasting plasma glucose (FPG) between 100 and 125 mg dL⁻¹ as a set criterion by American Diabetic Association (16),
3. Written informed consent (and assent when applicable) obtained from subject or subject's legal representative and ability for subject to comply with the requirements of the study.
4. blood pressure within the normal range (systolic blood pressure ≤ 140 mmHg, diastolic blood pressure ≤ 90 mmHg).
5. having no other health complications.

6.3 Exclusion Criteria

1. Pregnant, breastfeeding, or unwilling to practice birth control during participation in the study.
2. Presence of a condition or abnormality that in the opinion of the Investigator would compromise the safety of the patient or the quality of the data.
3. taking any treatment with either insulin or anti-diabetic drugs or any other natural health products known to impact blood sugar, or polyphenol absorption (e.g. fish oil).

4. Smoker.
5. having liver, thyroid, or significant gastrointestinal disorders.

7 CONCURRENT MEDICATIONS

All subjects should be maintained on the same medications throughout the entire study period, as medically feasible, with no introduction of new chronic therapies.

7.1 Allowed Medications and Treatments

Standard therapy for pre-diabetic is allowed except for treatments noted in the exclusion criteria described above and as noted in the prohibited medications section below.

7.2 Prohibited Medications and Treatments

The following medications are prohibited during the study and administration will be considered a protocol violation:

- any treatment with either insulin or anti-diabetic drugs.
- any other natural health products known to impact blood sugar, or polyphenol absorption (e.g. fish oil).
- Any liver, thyroid, or gastrointestinal disorders medications.

8 STUDY TREATMENTS

8.1 Method of Assigning Subjects to Treatment Groups

Up to 30 eligible patients will be randomly assigned to the dietary supplement seaweed or placebo treatment groups in a 1:1 ratio using a SAS-based computer-generated randomization scheme developed by a study investigator who will not be involved in data collection and analysis. Participants and other investigators will be blinded to which supplement is consumed each testing occasion for each participant until data analysis completed. At screening visit investigators will complete patient required data as detailed in the Study Manual, and fax it to the investigator who is responsible for randomization. The investigator who responsible for randomization will send back participants data encoded with numbers and supplements (intervention & placebo) with letters (A, B). Study intervention or placebo will be encapsulated in identical capsules and will be labelled with the letter A and B to conceal which supplement is given to each participants.

8.2 Blinding

Due to the objectives of the study, the identity of test and control treatments will not be known to investigators, research staff, or patients. The following study procedures will be in place to ensure double-blind administration of study treatments.

- Access to the randomization code will be strictly controlled.
- Packaging and labeling of intervention and placebo treatments will be encapsulated identically to maintain the blindness.

The study blind will be broken on completion of the clinical study and after the study database has been locked. Investigators will be aware of their subjects' treatment assignment after study statistical analysis completed.

During the study, the blind may be broken only in emergencies when knowledge of the patient's treatment group is necessary for further patient management. When possible, the Investigator should discuss the emergency with the Medical Monitor prior to unbinding. The pharmacist who is dispensing the study treatment will be available during study conduction and in case of any emergency, the pharmacist will disclose the blindness to medical monitor as it will be written in dispensing log in the research pharmacy.

8.3 Formulation of Test and Control Products

8.3.1 Formulation of Test Product

The intervention product used in this study is a dietary supplement extracted from seaweed called Ecklonia cava called "Seanol" that contain 13% phlorotannic polyphenol per capsule as stated by the manufacture company (Seanol inside, [name]). Other ingredients are dextrin, magnesium stearate and silica (in neglected percentage). The intervention supplement is encapsulated in vegetable cellulose that contains 500 Ecklonia cava extract (Seanol). This dose was selected to be similar to previous studies that shows no harm or sever adverse effect on participants (12, 14). The encapsulated product is brown-colored powder that requires no reconstitution.

Table X: Formulation and Measured pH of Dietary supplement (Seanol) and Placebo

	Dietary supplement (Seanol)	Placebo
Active Ingredient, mg/mL	13% phlorotannic polyphenol (include eckols, dieckol, 6,6'-bieckol, 8,8'-bieckol, phlorofucofuroeckol-A)	Dextrin
Other ingredient, mg/mL	80 % Dextrin magnesium stearate and silica (in neglected amount)	Non
pH		0.5 – 7.5

8.3.2 Formulation of Control Product

The placebo will be dextrin (BETA CYCLODEXTRIN, NF) will be ordered and provided by the study PI from a pharmaceutical company "MEDISCA" (<https://www.medisca.co.uk/>). Dextrin was selected to account for the similar complex carbohydrate content of the intervention supplement. Placebo will be encapsulated in vegetable cellulose capsules that is identical in size and coultre to the intervention capsules

8.3.3 Packaging and Labeling

Packaging: Study drug is supplied in a bottle containing 60 single use capsules. The capsules will be packaged in enclosed within a laminated foil pouch bottle.

Labeling: Each bottle of study drug will be labeled with the required FDA warning statement, the protocol number, a treatment number, the name of the principle investigator, and directions for patient use and storage. direction for both study test and placebo will be the same as both has the same direction which will ensure blinding in the study.

8.4 Supply of Study Drug at the Site

The principle investigator will ship Study Drug to the investigational sites. The initial study drug shipment will be shipped after site activation. Subsequent study drug shipments will be made after site request for resupply.

8.4.1 Dosage/Dosage Regimen

The study test is a dietary supplement called brown seaweed (*Ecklonia cava*) which will be given at 580 mg dose. Seaweed will be administered only one time at the only one visit to investigate the acute effect of the investigational product. administration will be orally.

The placebo is a plain dextrin will be given at 500 mg dose. Placebo will be administered only one time at the only one visit to investigate the acute effect of the investigational product. administration will be orally.

8.4.2 Dispensing

The pharmacists at research pharmacy at KKHU will be the only pharmacist at hospital who are responsible for study treatment or placebo dispensing.

8.4.3 Administration Instructions

The study dietary supplement (seaweed) or placebo will be administered to patient at the study site only one time at a supervision of study investigator and medical monitor where the patient will be instructed to administer the study capsules orally.

8.5 Supply of Study Drug at the Site

Study dietary supplement will be supplied to the pharmacy of research at study site (KKUH) by the principle investigator of the study. If more participants needed as a replacement of withdrawn participants, study treatment will be stored at the pharmacy of research at KKHU which will be available for the new participants.

8.5.1 Storage

Study dietary supplement should be stored by the study site at controlled room temperature, 15 to 30°C (59 to 86°F). If the temperature of study drug storage in the pharmacy exceeds or falls below this range, this will be reported to the study PI or designee and captured as a deviation. The supplement will be stored in original packaging (foil pouch and protected from light) at room temperature according to the instructions outlined on the Drug Administration Instructions.

8.6 Study Drug Accountability

An accurate and current accounting of the dispensing and return of study drug for each subject will be maintained on an ongoing basis by a member of the study site staff. The number of study drug dispensed and returned by the subject will be recorded on the Investigational Drug Accountability Record. The study monitor will verify these documents throughout the course of the study.

8.7 Measures of Treatment Compliance

Not applicable due to that study dietary supplement (seaweed) or placebo will be administered to patient at the study site only one time at a supervision of study investigator.

9 STUDY PROCEDURES AND GUIDELINES

A Schedule of Events representing the required testing procedures to be performed for the duration of the study is diagrammed in Appendix 1.

Prior to conducting any study-related activities, written informed consent and the Health Insurance Portability and Accountability Act (HIPAA) authorization must be signed and dated by the subject. If appropriate, assent must also be obtained prior to conducting any study-related activities.

9.1 Clinical Assessments

9.1.1 Concomitant Medications

All concomitant medication and concurrent therapies will be documented at Baseline/Screening. Dose, route, unit frequency of administration, and indication for administration and dates of medication will be captured.

9.1.2 Demographics

Demographic information (date of birth, gender, race) will be recorded at Screening.

9.1.3 Medical History

Relevant medical history, including history of current disease, other pertinent respiratory history, and information regarding underlying diseases will be recorded at Screening.

9.1.4 Physical Examination

A complete physical examination will be performed by either the investigator or a subinvestigator who is a physician at screening. Qualified staff (MD, NP, RN, and PA) may complete the abbreviated physical exam at all other visits. New abnormal physical exam findings must be documented and will be followed by a physician or other qualified staff at the next scheduled visit.

9.1.5 Vital Signs

Body temperature, blood pressure, pulse and respirations will be performed after resting for 5 minutes at all Visits.

9.1.6 Adverse Events

Information regarding occurrence of adverse events will be captured throughout the study. Duration (start and stop dates), severity outcome, treatment and relation to study drug will be recorded on the case report form (CRF).

9.2 Pharmacokinetic Measurements

NA

9.3 Research Laboratory Measurements

9.3.1 Blood profile

Blood will be obtained and sent to the site's clinical chemistry lab for determination of random glucose, fasting blood glucose and insulin level.

10 EVALUATIONS BY VISIT

10.1 Visit 1 (Day1 /Week 1/Month 1)

1. Review the study with the subject (subject's legal representative) and obtain written informed consent.
2. Assign the subject a unique screening number.
3. Record demographics data.
4. Record medical history, including a history of pre-diabetic, diagnosis date.
5. Perform a complete physical examination.
6. Perform and record vital signs.
7. Perform and record results of blood pressure testing.
8. Collect blood for clinical laboratory tests (baseline of blood glucose level).
9. Schedule subject for Visit 2 in different days.
10. List all additional procedures, such as Randomize subject

10.2 Visit 2

1. Perform abbreviated physical examination.
2. Perform and record vital signs.
3. Collect blood for clinical laboratory tests (baseline of blood glucose and insulin levels).
4. Administer either study dietary supplement (seaweed) or placebo based on blinded randomization.
5. Perform carbohydrates ingestion
6. Collect blood for clinical laboratory tests (blood glucose and insulin levels 30 min after administration of study treatment).
7. Collect blood for clinical laboratory tests (blood glucose and insulin levels 60 min after administration of study treatment).
8. Collect blood for clinical laboratory tests (blood glucose and insulin levels 90 min after administration of study treatment).
9. Collect blood for clinical laboratory tests (blood glucose and insulin levels 120 min after administration of study treatment).

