3.2 Secondary Objectives

Investigate the safeness and potential adverse effect of applying sea weed (E. cava) as a therapeutic diet composition on patient with pre-diabetes, compared to placebo.

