10.3 Early Withdrawal Visit

1. Record any Adverse Experiences
2. Perform complete physical examination.
3. Perform and record vital signs.

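### Visit 2 vital signs are scheduled only before the single dose, so they cannot contribute to the safety comparison with placebo

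*Combined protocol and SAP*

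**What the plan says.** Section 10.2 is a numbered list of nine steps for Visit 2, the dosing visit. Step 1 is "Perform abbreviated physical examination" and step 2 is "Perform and record vital signs". Step 3 is the baseline glucose and insulin sample. Step 4 is "Administer either study dietary supplement (seaweed) or placebo based on blinded randomization", and step 5 is the carbohydrate load. Steps 6 to 9 are blood draws at 30, 60, 90 and 120 minutes, and the list ends with "Collect blood for clinical laboratory tests (blood glucose and insulin levels 120 min after administration of study treatment".

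The general rules give no time relative to the dose. Section 9.1.5 says "Body temperature, blood pressure, pulse and respirations will be performed after resting for 5 minutes at all Visits". Section 9.1.4 says "Qualified staff (MD, NP, RN, and PA) may complete the abbreviated physical exam at all other visits". Appendix 1 carries one untimed vital-signs mark for Visit 2.

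Section 10.3 asks for vital signs, and for staff to "Perform complete physical examination", but only at an early withdrawal visit.

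The secondary objective (3.2) is to "Investigate the safeness and potential adverse effect of applying sea weed" in comparison with placebo. Section 14.3 says safety and tolerability data are summarised by treatment group.

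**The concern.** A safety measurement can inform a comparison between arms only if some of it is taken after the arms have been treated differently. Here the vital signs come at screening and again just before the capsule. At both times every participant is untreated, so any difference between arms is chance imbalance at baseline.

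What is at stake is modest but real. Section 5.2 asks participants to rate cardiac palpitations and balance disorders, yet no scheduled pulse or blood pressure stands beside those answers. Section 11.1 counts unfavourable signs as adverse events, but a change in pulse or blood pressure without symptoms would not be picked up by any scheduled measurement. The safety interim in 14.5, held when about half the participants have completed Visit 2, would have no scheduled post-dose vital signs from completers either. The trial already bears most of the burden of collecting these data; their timing leaves them silent on treatment.

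**Working it through.** **The plan's own figures.** The plan gives no calculation for vital signs. Its only design calculation is the sample size in 14.6: 2 × 32² × (1.96 + 0.84)² / 38² = 16056.32 / 1444 = 11.12, which rounds up to 12 per group. The document prints 11.11, a truncation that changes nothing. The point does not depend on this figure. The planned enrolment is up to 30 at 1:1 (8.1), so 30 / 2 = 15 per arm.

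**Is the 10.2 list in time order?** Yes. Baseline blood precedes dosing, and the later draws are labelled by minutes after it.

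**Count of what follows the dose at step 4:**

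| Item in 10.2 | At or before step 4 | After step 4 |
|---|---|---|
| Vital signs | 1 (step 2) | 0 |
| Physical examination | 1 (step 1) | 0 |
| Blood draws | 1 (step 3) | 4 (steps 6–9) |

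**Could another section supply a post-dose set for completers?**

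- 9.1.5 requires vital signs at each visit. The step 2 set satisfies it.
- 9.1.4 concerns the examination and gives no time relative to dose.
- Appendix 1 has one untimed mark for Visit 2, also satisfied by step 2.
- The synopsis gives one day of follow-up. The only assessment placed in that period is the self-rated questionnaire (5.2).
- 10.3 applies only to participants who leave early.

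Result: 0 scheduled post-dose vital-sign sets per completer, hence 0 of up to 30.

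**What one repeat set would provide.** The quantity of interest is the between-arm difference in pre-to-post change. A within-arm change would mix any product effect with the carbohydrate load, repeated sampling and time at rest, all of which both arms share. With n per arm and SD of change s:

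half-width of the 95% CI = t(0.975, 2n − 2) × s × √(2/n)

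With n = 15, t(0.975, 28) = 2.048 and √(2/15) = 0.365, so the half-width is 0.748 × s.

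- s = 8 mmHg: 5.98 mmHg
- s = 10 mmHg: 7.48 mmHg

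The documents give no SD for change in blood pressure, so 8 to 10 mmHg is an assumption. The same multiplier applies to pulse, with whatever SD is assumed for it.

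**Does it fit the session?** The synopsis gives 3 hours. Sampling takes 120 minutes, leaving 180 − 120 = 60 minutes for everything else. A repeat set with the 5-minute rest in 9.1.5 needs roughly 5 to 10 of those minutes.

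**The case against.** The strongest reply is that no planned analysis loses an input. Section 5.3 names glucose limits and adverse events as the safety evaluations, and 14.4 analyses intolerance scores and adverse events. Vital signs are nowhere named as a safety outcome, so using them only as a baseline check is coherent. This stands, and it is why the point is an inexpensive improvement and not a flaw in a specified analysis. It does not remove the point: the objective is comparative safety, and the trial already takes these measurements on the dosing day.

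Second, the added estimate would be imprecise, and no document reports a blood-pressure effect to look for. That also stands; the repeat would be descriptive.

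Third, silence in 10.2 is weak evidence. Appendix 1 requires height, weight, medication review and adverse-event recording at Visit 2, none of which 10.2 lists. So the accurate statement is that no completer is scheduled to have a post-dose set. Unscheduled checks remain possible, but checks prompted by events would not give comparable data by arm.

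A reader might infer from 10.2 that adverse events are not asked about after dosing. The documents do not support that: 11.1 has the investigator probe for them at each visit, 9.1.6 captures them throughout, and Appendix 1 marks them at Visit 2.

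A reader might also infer a biased contrast between early leavers, who get a post-dose set under 10.3, and completers. That is nearly hypothetical. There is one supervised dose and about two hours of sampling, and the withdrawals described in 12.2 occur before Visit 2.

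**Conclusion.** The point holds for vital signs. Section 10.2 places them before the single dose, no other section schedules them afterwards for completers, and they cannot inform the comparison in 3.2. The count, 0 of up to 30, rests on the text alone. The precision of a repeat, about 6.0 to 7.5 mmHg for blood pressure, rests on the assumed SD of change and on 15 per arm providing data.

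The safety comparison is not empty, and it would be too strong to say that it rests on self-report alone apart from glucose. Adverse events include signs and laboratory findings (11.1), are graded for severity (11.1.1) and are assessed for relationship to the product (11.1.2). What is missing is a scheduled post-dose vital-sign measurement.

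The examination is likewise scheduled only before the dose, but it does not follow that it should be moved. Step 1 is the only examination on the dosing day before the capsule. Moving it would give up that check, and a post-dose abbreviated examination would then have only a complete examination from an earlier day to set against it.

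**What to change.** Leave steps 1 and 2 of 10.2 as they are, so that the pre-dose vital signs serve as baseline. Add one step after the 120-minute sample that repeats the four measurements listed in 9.1.5 under the same rest condition. Mark that time point separately in Appendix 1. In the analysis plan, add a descriptive summary by arm of the pre-to-post change in each measurement, with the between-arm difference and its 95% CI, and no hypothesis test.

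The cost is roughly 5 to 10 minutes per participant including the rest, with the same staff and inside the 3-hour session, plus one descriptive table.

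If the sponsor prefers not to add the measurement, 9.1.5 and Appendix 1 should at least say that vital signs are baseline data only, so that nobody expects them in the safety comparison.

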10.3 Early Withdrawal Visit

1. Record any Adverse Experiences
2. Perform complete physical examination.
3. Perform and record vital signs.

11 ADVERSE EXPERIENCE REPORTING AND DOCUMENTATION

11.1 Adverse Events

An adverse event (AE) is any untoward medical occurrence in a clinical investigation of a patient administered a pharmaceutical product and that does not necessarily have a causal relationship with the treatment. An AE is therefore any unfavorable and unintended sign (including an abnormal laboratory finding), symptom or disease temporally associated with the administration of an investigational product, whether or not related to that investigational product. An unexpected AE is one of a type not identified in nature, severity, or frequency in the current Investigator's Brochure or of greater severity or frequency than expected based on the information in the Investigator's Brochure.

The Investigator will probe, via discussion with the subject, for the occurrence of AEs during each subject visit and record the information in the site's source documents. Adverse events will be recorded in the patient CRF. Adverse events will be described by duration (start and stop dates and times), severity, outcome, treatment and relation to study drug, or if unrelated, the cause.

11.1.1 AE Severity

The National Cancer Institute's Common Terminology Criteria for Adverse Events (CTCAE) Version 3.0 should be used to assess and grade AE severity, including laboratory abnormalities judged to be clinically significant. The modified criteria can be found in the study manual. If the experience is not covered in the modified criteria, the guidelines shown in Table 1 below should be used to grade severity. It should be pointed out that the term "severe" is a measure of intensity and that a severe AE is not necessarily serious.

Table 1. AE Severity Grading

Severity (Toxicity Grade)	Description
Mild (1)	Transient or mild discomfort; no limitation in activity; no medical intervention or therapy required. The subject may be aware of the sign or symptom but tolerates it reasonably well.
Moderate (2)	Mild to moderate limitation in activity, no or minimal medical intervention/therapy required.
Severe (3)	Marked limitation in activity, medical intervention/therapy required, hospitalizations possible.
Life-threatening (4)	The subject is at risk of death due to the adverse experience as it occurred. This does not refer to an experience that hypothetically might have caused death if it were more severe.

